**b. Drugs to be used**

There will be no drugs used in this study.

**c. Devices to be used**

There will be no devices used in this study.

**d. Procedures/surgical interventions**

At baseline, post-intervention, and 3 months following the end of the intervention, participants will be asked to complete a dried blood spot sample collection using a minimally invasive finger skin prick technique, which involves pricking the finger with a lancet, milking the finger to produce 5-10 drops of blood onto filter paper, allowing the blood spots to dry, and mailing it to the study team at MGH in a secure envelope. Prior to the start of the intervention, an RA will guide the participant in self-collecting blood samples via a videoconference call or phone call (per the participant's preference). Participants will also be sent written instructional handouts. The RA will ask the participant a series of questions to gauge understanding, provide corrective feedback, and answer any questions the participant might have before proceeding to guide the participant in the procedure.

Participants will be asked to allow the sample to dry overnight, document the date the sample was taken on the filter paper, and mail it to the study team at MGH the next morning. Samples will be received by the RA, who will mark the date of receipt in the study database. Samples can be in ambient air for up to 2 weeks without degradation. We will ask participants to mail the samples within 24 hours of taking them to minimize the time samples are in ambient air. If samples are received beyond 2 weeks of the date indicated on the filter paper, we will ask participants to provide another sample, and participants will be made aware of this possibility in the consent form. Once received, the RA will bring the samples to be stored in a -20°C freezer in the MGH Clinical Research Center lab or mail them to our collaborator at the Laboratory for Human Biology Research at Northwestern University for storage and processing. Blood spots can be frozen at this temperature for several years without degradation.

When initially mailing the blood spot kit to participants, the RA will indicate the participant's study ID number, group assignment, date, and data collection timepoint on the filter paper. Participants will be informed not to write any personally identifying information on the filter paper. This will keep the blood samples de-identified.

Collecting whole blood spots with filter paper has been used in hospitals for decades to collect blood from newborns, and it has proven to be a safe and effective means for collecting and transporting samples in several large NIH-funded field-based studies. The Centers for Disease Control and Prevention have maintained independent quality control efforts and have reported that these

approaches can achieve the same level precision and reproducibility of standard blood collection methods. Our collaborators at Northwestern University have pioneered this technique as leaders in the development, validation and application of whole dried blood spots as a convenient means for collecting, transporting, and processing blood samples from community settings and mind-body intervention research including clinical trials. We used these methods in our recent open pilot trial and found promising feasibility and acceptability in this population (IRB Protocol Number 2020P000045). The dried blood spot samples will be collected using a commercially available, FDA approved Whatman™ 903 Proteinsaver cards and BD Microtainer® Contact-Activated Lancets (gauge 14, incision depth 2mm (8/10")). The samples will not undergo CLIA tests and will be stored for approximately 1-2 years.

There will be no surgical interventions for this study.

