#### **IV. SUBJECT ENROLLMENT**

**a. Methods of enrollment, including procedures for patient registration and or randomization**

Study staff will approach patients about participating in the study using one the modalities discussed in section III.b. For patients who are not interested in participation, study staff will discontinue contact. For patients who are interested in participation, study staff will screen patients for eligibility (criteria detailed in section III.a). If a patient screens as eligible, they will be asked to provide informed consent using one of the procedures detailed in section IV.b. Following informed consent patients will be 1:1 randomized (see section IV.c) and enrolled in the study using a random number generator.

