## **IX. MONITORING AND QUALITY ASSURANCE**

**a. Independent monitoring of source data**

Source materials will include information collected from survey questionnaires at baseline, post-intervention, and 3-month follow-up; exit interviews; weekly practice logs; post-session surveys; and blood spot collection procedures. All self-

report questionnaires will be entered electronically via REDCap. Individual exit interviews will be conducted by phone or videoconferencing. Upon their receipt, all dried blood spot samples will be stored securely in an MGH affiliated lab, on the MGH campus. Samples will later be shipped, in accordance with MGB and CDC guidelines, to our collaborators [name] and [name] at Northwestern University for storage and/or processing. All samples will be labeled with the patient ID, date of collection, group assignment, and time point (baseline, post-intervention, 3-month follow-up). We will follow all CDC shipping guidelines (e.g., placing a freeze pack inside of an insulated shipping container, placing sealed plastic bags containing the samples into a box). We will seal the box tightly with tape and ship specimens via courier to [name] in Health Lab at the Northwestern University Feinberg School of Medicine.

[name] will securely store the samples in his locked lab at Northwestern before bringing them for processing to his collaborator [name] at the Laboratory for Human Biology Research at Northwestern University. The blood samples will not contain identifiers that could be used by the outside collaborators to link the data to individual subjects; they will be labeled with participants' study ID numbers and not any personally-identifying information, and only Partner's study staff will have access to the data file linking participant's personal information to their study ID number. Study staff have completed CDC and HealthStream trainings on dried blood spot storage and shipping and have acquired the proper documentation to ship samples to a non-MGB lab.

All information collected will be for the purposes of research and will only be accessible to study staff and stored securely on the Partners' network. Survey and practice log data will be reviewed for completeness though participants will be allowed to skip any questions they are not comfortable answering.

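### Blood spot cards carry the treatment arm to the assay laboratory, although study ID, collection date and timepoint would be enough to identify them.

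*Combined protocol and SAP*

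**What the plan says.** Section V.d (Procedures/surgical interventions) sets out what the research assistant writes on each card when the kit is first sent: "study ID number, group assignment, date, and data collection timepoint on the filter paper". Section IX.a (Independent monitoring of source data) says the same of stored and shipped material: "All samples will be labeled with the patient ID, date of collection, group assignment, and time point". Section IV.a places allocation straight after consent ("Following informed consent patients will be 1:1 randomized"), so the arm can be known when the baseline kit is prepared.

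Both sections send the cards to collaborators at an outside university for storage and processing. Section IX.a describes the safeguard as follows: "The blood samples will not contain identifiers that could be used by the outside collaborators to link the data to individual subjects". It adds that only "study staff will have access to the data file linking" personal information to the study ID. Neither section says that the arm is coded, covered or removed before assay.

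On late cards, section V.d says: "If samples are received beyond 2 weeks of the date indicated on the filter paper, we will ask participants to provide another sample". The blood spot paragraphs in sections V.a and V.e place the baseline card in the week before the intervention. No section says how a replacement taken after that week is classified.

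**The concern.** Removing names from a card is not the same as masking the arm. Anyone who handles a card at the laboratory can read which programme the participant attended. So can whoever decides whether a sample is adequate, which Table 1 counts as a feasibility outcome with a benchmark of 80%. The documents do not say who makes that decision. IL-6, CRP and TNF-alpha are the only laboratory-measured outcomes in Table 2, and they are the ones that can be masked most easily. Leaving the arm on the label keeps open an avoidable route to handling cards differently by arm, such as in accepting, rejecting or repeating a sample.

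A smaller matter concerns the same cards. If a baseline card arrives too late, its replacement may be collected when the programme is already under way, and the text does not say what that value then represents.

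**Working it through.** The documents give no figure to reproduce for this point. The label question rests on setting the sections side by side, and the replacement question rests on dates.

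**Label**

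- What is on the card: study ID, arm, date and timepoint (V.d and IX.a agree).
- Where the card goes: to the outside laboratory, either directly or after storage at the hospital (V.d, IX.a).
- What is withheld from the laboratory: personal identity and the file that links identity to study ID (IX.a).
- What identifies a card uniquely: study ID with timepoint, and the collection date separates a repeat card from the one it replaces. The arm adds nothing to this, and the documents state no use for it on the card.

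The arm is therefore disclosed to the laboratory, and no stated procedure needs it there.

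**Replacement timing (secondary)**

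Inputs: eight weekly sessions (V.a); a baseline card in the week before the intervention (V.a, V.e); a request for another sample once receipt is more than 14 days after the date on the card (V.d). Take session 1 as day 0, so that sessions fall on days 0, 7, 14, ..., 49. The baseline window is then day -7 to day -1.

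Earliest day on which a card is late = collection day + 15. A same-day replacement is the best case.

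- Taken on day -7: -7 + 15 = day +8. The sessions on days 0 and 7 have passed.
- Taken on day -1: -1 + 15 = day +14. The same two sessions have passed, and the third is held that day.
- For a replacement by day 0, the first card must be taken by 0 - 15 = day -15, which is 8 days before the window opens.
- Even with the survey window of up to two weeks, a card taken on day -14 gives -14 + 15 = day +1.

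Post-intervention cards show the same pattern. A card taken 0 to 7 days after the last session is replaced 15 to 22 days after it at the earliest, at least 15 - 7 = 8 days outside the one-week window.

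Size per card, if such a replacement were analysed as baseline: assume that a marker changes linearly from session 1 to session 8 and by the same amount in every participant. The share of change already past is 8/49 = 16% to 14/49 = 29%. Baseline cards per arm range from 15 (75% of 20, at N=40) to 25 (all of 25, at N=50). One such card would shrink the arm's mean change by 16.3%/25 = 0.7% to 28.6%/15 = 1.9%. If change comes later, the figure is close to zero. The documents give no rate of late cards, so no total can be derived.

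**The case against.** The strongest reply is that the label hardly touches a planned analysis. Aim 2 looks at change within each group, and no test of biomarkers between arms is planned. For a within-group change, the knowledge that could matter most at the laboratory is the timepoint, and that stays on the card. The documents promise de-identification and deliver it; they promise no masking. All of this stands, and it is why the point is minor. It does not give the arm a purpose on the label, and removing it is close to free.

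A reader might infer that the biomarker results or the card-quality rates will be biased by arm. The documents do not support that. Assay readings are unlikely to depend on the label, and nothing shows that quality would be judged differently by arm.

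A reader might also infer that the late-card rule routinely turns baseline cards into on-treatment ones. That does not follow either. It needs a card that arrives more than two weeks after collection, and the protocol works against this: "Prior to the start of the intervention, an RA will guide the participant in self-collecting blood samples", and "We will ask participants to mail the samples within 24 hours of taking them to minimize the time samples are in ambient air". The baseline window already excludes a card taken after session 1, collection dates are recorded, and a mixed model fitted by maximum likelihood can take a missing baseline value. Most analysts would handle such a card sensibly. What remains is a missing sentence.

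**Conclusion.** The point holds as a minor, avoidable weakness in the labelling. The arm is on every card that reaches the assay laboratory, the only safeguard concerns identity, and no stated procedure needs the arm there. This follows from the text of sections V.d and IX.a and needs no assumption. The effect on results is probably small and cannot be quantified from the documents. It is confined to exploratory within-group biomarker changes and to the card-quality count, and it does not threaten the main feasibility conclusions.

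The replacement question is a clarification and does not carry the point. The dates are firm given weekly sessions and the stated window: no late in-window baseline card can be replaced before session 1 under the stated trigger. The 0.7% to 1.9% per card depends on equal linear change and on an analyst setting aside the protocol's own baseline window.

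**What to change.** In sections V.d and IX.a, list only study ID, collection date and timepoint on the card, and keep the arm in a file held by study staff, who already hold the restricted linking file. State that laboratory staff and whoever judges sample quality do not have access to the arm. This masks arm but not before versus after.

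In section V.d, add that a replacement for a late baseline card, if collected after session 1, falls outside the baseline window of sections V.a and V.e and is not analysed as baseline. In section VI.c, say that the baseline value is then treated as missing in the mixed model, because the present missing-data sentence speaks only of dropouts. The participant then contributes no change score for that marker.

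The cost is a revised label and two or three sentences. The only loss is a few missing baseline biomarker values, if late cards occur.

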**e. Data to be collected and when the data is to be collected**

The self-report survey measures will be the same for the MBCT and control groups. The surveys will be administered within approximately 1-2 weeks before and after the intervention and at 3 months post-intervention. This battery will include the following validated self-report surveys: Assessment of Survivor Concerns (fear of recurrence), CAMS-R (mindfulness), Cardiac History and Symptoms, Current Experiences Scale (CES; resiliency), COVID items, demographic questionnaire, Expectancy Questionnaire, Experiences Questionnaire (decentering), Group cohesion scale, Hospital Anxiety and Depression Scale (HADS; depression and anxiety), Interpersonal Reactivity Index (IRI; empathy), MAIA-2 body subscales (interoception), MBCT-AS Checklist (fidelity checklist), PHQ-9 (depression), Medical Outcomes Study – Specific Adherence Scale (MOS-SAS; health behaviors), one item from the Short Form-12 (SF-12), Self-Other Four Immeasurables (SOFI; self and other compassion), PROMIS Physical Function (PROMIS-PF; physical function), and The Positive and Negative Affect Schedule-Positive Affect (PANAS-PA). The post-intervention survey will also include a group cohesiveness measures to assess perceived connection with other group members as well as intervention satisfaction questions to assess acceptability. The 3-month follow-up survey will include questions about continued mindfulness practice. The baseline survey, post-intervention survey and post-intervention survey will all include questions related to COVID-19. All three survey batteries are included in the IRB submission.

At the end of each session all participations will complete a post-session survey assessing session likes and dislikes. Between each session intervention participants will be asked to complete home practice logs documenting the frequency of and the thoughts related to their weekly mindfulness practice.

Upon completion of the intervention, participants from both the intervention and control group will be asked to complete a 30-60-minute exit interview via phone or videoconference.

Both intervention and control group participants will be asked to provide dried blood spot samples within one week before and after the intervention and 3-months-post intervention. Samples will be used to examine IL-6, CRP, and TNF- $\alpha$  levels.

Data collection will also consist of viewing and extracting data from the EHR to assess medical and demographic variables (e.g. medical diagnoses, medications, cardiac rehab attendance) and/or confirm eligibility. REDCap is a secure online data collection system.

[figure not shown]

Figure 1. Overview of pilot RCT data collection procedures

## VI. BIOSTATISTICAL ANALYSIS

### a. Specific data variables being collected for the study

The primary outcomes are feasibility and acceptability of the intervention and research procedures (Table 1). Study staff will record all feasibility outcomes throughout recruitment, screening, enrollment, and the intervention, data collection, and follow-up phases.

Table 1. PRIMARY OUTCOMES	
Feasibility	
Recruitment	$\geq 70\%$ consent to screening; $\geq 70\%$ meet screening criteria; $\geq 70\%$ of eligible enroll; enroll $\geq 20$ participants/month
Eligibility criteria	$< 20\%$ ineligible due to each criterion; reasons for ineligibility; reasons for refusal; characteristics of refusers
MBCT and control interventions	Adherence: $\geq 75\%$ session attendance; retention: $\geq 75\%$ post-assessments, $\geq 70\%$ follow-up assessments completed; fidelity: checklist score $\geq 80\%$ ; $\geq 75\%$ complete home practice at least 3 days/week
Videoconferencing	$< 20\%$ of connections dropped during session; $< 20\%$ of sessions missed due to technical problems; number ( $M < 2.0$ ) and type of problems; $< 20\%$ ask for extra training, type of extra training needed
Blood spots	Adherence: $\geq 75\%$ submitted at baseline, post-intervention, $\geq 60\%$ submitted at follow-up; 80% adequate quality
Acceptability	
MBCT and control interventions	Session satisfaction and helpfulness, enjoyment, relevance, utility of each session component (1=not at all, 10=very much; $M \geq 7.5$ ; post-session survey ); overall program satisfaction ( $M \geq 7.5$ ), $\geq 75\%$ plan to use the skills, $\geq 75\%$ would recommend the program to others ( post-intervention )

	survey); likes, dislikes, suggestions for improvement (exit interview); <math>\geq 60\%</math> continue meditation practice (follow-up survey)
Videoconferencing	Ease and confidence of use (1=not at all, 10=extremely <math>M \geq 7.5</math>), interference of technical problems (1=none, 10=extreme; <math>M < 2.0</math>), audiovisual quality and overall satisfaction (1=poor, 10=excellent; <math>M > 7.5</math>; post-session survey); pros and cons, suggestions for improvement (exit interview)
Blood spots	Ease of data collection and submission (1=not at all, 10=extremely; <math>M \geq 7.5</math>), level of pain (1=none, 10=extreme; <math>M < 2.0</math>; post-intervention survey); concerns, suggestions for improvement (exit interview)

*Note.* M = mean. Benchmarks are informed by my pilot data, prior literature and prior clinical trials.

The exploratory outcomes are within-group changes in health-related variables, measured at baseline, post-intervention, and 3-month follow-up. All self-report measures are validated (Table 2).

Table 2. EXPLORATORY OUTCOMES	
Variable	Measurement
Fear of Recurrence	Assessment of Survivor Concerns
Mindfulness	CAMS-R
Resiliency	Current Experiences Scale (CES)
Decentering	Experiences Questionnaire
Depression and Anxiety	Hospital Anxiety and Depression Scale (HADS)
Empathy	Interpersonal Reactivity Index (IRI)
Interoception	MAIA-2 body subscales
Fidelity checklist	MBCT-AS Checklist
Depression	PHQ-9
Health behaviors	Medical Outcomes Study – Specific Adherence Scale (MOS-SAS)
Everyday health	One item from the Short Form-12 (SF-12)
Social connectedness	Self-Other Four Immeasurables (SOFI)
Physical function	PROMIS- Physical Function (PROMIS-PF)
Positive Affect	The Positive and Negative Affect Schedule-Positive Affect (PANAS-PA)
IL6, TNF- $\alpha$ , CRP	Whole dried blood spots

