**Version Date: 12/07/2021**

**I. BACKGROUND AND SIGNIFICANCE**

**a. Historical Background**

**It is critical to treat depression in patients with acute coronary syndrome (ACS).** Among the one million ACS patients in the U.S. each year (e.g., myocardial infarction, unstable angina), up to 45% have elevated depression symptoms. Even mild elevations in depression symptoms double the risk of mortality after ACS. Meta-analyses of over 4,000 ACS patients and 53 studies have found that depression is an independent risk factor for recurrent cardiac events, re-hospitalizations, cardiac mortality, and all-cause mortality, beyond other traditional risk factors. Left untreated, depression persists for years and doubles the risk of death through biological and behavioral mechanisms. Biologically, depression causes inflammation through neuroendocrine alterations, leading to atherosclerotic plaque formation and rupture. Behaviorally, ACS patients need to make multiple lifestyle changes, but depression symptoms (e.g., disinterest, lack of motivation) prevent engagement in cardiac health behaviors (e.g., physical activity, diet). Thus, depression treatment is necessary to promote biological and behavioral changes important for survival.

**Depression treatments for ACS patients need improvement.** More ACS patients prefer psychological (75%) rather than pharmacological depression treatments (20%). However, the recommended psychological intervention, cognitive-behavioral therapy (CBT), has limited effects on depression and cardiac outcomes. Targeting the mechanisms that link depression to ACS could improve treatment efficacy, but CBT does not aim to target a key mechanism, i.e., inflammation. Consistent evidence from multiple meta-analyses suggests that depression is associated with elevated levels of inflammatory cytokines, particularly C-reactive protein (CRP), interleukin-6 (IL-6), and TNF- $\alpha$ . These same specific cytokines are also elevated, positively correlated with depression symptoms, and independently increase the risk of mortality in patients with cardiac disease. Of note for depression treatment, the relationships are bidirectional: treating depression reduces inflammation, but reducing inflammation also reduces depression symptoms, making CRP, IL-6, and TNF- $\alpha$  salient treatment targets for both depression and cardiac health in ACS patients.

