## III. SUBJECT SELECTION

### a. Inclusion/exclusion criteria

#### **Inclusion criteria:**

1. Lifetime ACS per medical record and/or patient confirmation
2. Current elevated depression symptoms (PHQ-9 $\geq$ 5)
3. Age 35-85 years
4. Access to high-speed internet
5. Massachusetts General Brigham patient

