**d. Psychosocial risks**

Patients may experience discomfort from completing the survey questionnaires or exit interview and/or participating in the intervention mindfulness trainings or discussions. Participants who do not find the study to provide a benefit to them may find this upsetting as well. All possible measures will be taken to ensure patient comfort and participants will be informed that they could exit the study at any point with no penalty. The PI (licensed clinical psychology) will be available while intervention groups are being conducted to intervene if needed (due to patient discomfort or to answer specific questions about the study). Participants will be informed that they can choose not to complete any surveys or answer any specific survey items or exit interview questions that make them feel uncomfortable, and that they do not need to complete the blood spot procedures. All of these procedures are consistent with sound research design and do not unnecessarily expose subjects to risk.

The main psychosocial safety concern related to patients in this study is worsening depression symptoms and/or suicidal ideation. Subject safety regarding mood and suicidal ideation will be ensured in several ways.

First, eligibility criteria require that patients do not have active suicidal ideation at the time of enrollment, and that they have not been hospitalized for a psychiatric reason in the past year. Thus, it is not likely that participants will report active suicidal ideation during or following the intervention. Moreover, our eligibility criteria require only minimal depression symptoms and thus we do not expect to have a severely depressed sample.

During the eligibility screening procedures, participants will be administered the Patient Health Questionnaire-9 (PH-9) over the phone. If any patient endorses suicidality (i.e., PHQ-9 item 9 score above 0; “Over the past two weeks, how often have you been bothered by thoughts that you were better off dead or of hurting yourself in some way”), the RA will follow our standardized safety assessment protocol that our team has developed and used in prior funded studies of ACS patients with elevated depression symptoms. The protocol involves further assessing safety risks through a series of structured questions, with

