**b. Potential benefits to society**

Developing targeted, efficacious, and accessible interventions to treat depression in ACS patients may have important public health benefits. Depression is common and deadly among acute ACS patients with up to 45% experiencing at least mild depression symptoms. Even mild depression symptoms double the risk of death in ACS patients. Mind-body interventions that are accessible and address the underlying pathophysiology of comorbid depression and cardiovascular disease are needed, and the MBCT intervention being tested in the current study has the potential to address this need. This study will establish the feasibility and acceptability of the intervention and inform targets for refinement in a future R01 efficacy trial. Thus, participation in this study may result in the development of an innovative, efficacious, and accessible depression treatment that can have substantial benefit to future ACS patients.

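### Two primary recruitment benchmarks count the PHQ-9 ≥5 criterion itself, and both would be missed if the screened pool resembles the only prevalence the plan gives (up to 45%)

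*Combined protocol and SAP*

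**What the plan says.** Section VI.a makes feasibility a primary outcome and sets its benchmarks in Table 1. The Recruitment row asks that at least 70% of patients meet the screening criteria, alongside separate targets for consent to screening, enrolment of eligible patients and monthly enrolment. The Eligibility criteria row asks for under 20% "ineligible due to each criterion; reasons for ineligibility; reasons for refusal; characteristics of refusers". No criterion is exempted. The table does not say over whom these two shares are counted. The note under it says: "Benchmarks are informed by my pilot data, prior literature and prior clinical trials". It gives no screening yield or PHQ-9 pass rate.

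Section III.a lists "Current elevated depression symptoms", defined as PHQ-9 ≥5, as an inclusion criterion. Section VII.d places the test at screening: "During the eligibility screening procedures, participants will be administered the Patient Health Questionnaire-9". Section III.b does the same for inpatients.

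The document gives one prevalence, twice. Section I.a says that among ACS patients "up to 45% have elevated depression symptoms", and section VIII.b says: "Depression is common and deadly among acute ACS patients with up to 45% experiencing at least mild depression symptoms". Neither attaches an instrument or a cut-off.

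**The concern.** PHQ-9 ≥5 is not an incidental exclusion. It selects the patients the intervention is for, and in an ACS population many patients will not have it. Both benchmarks nevertheless treat failing it like any other reason for ineligibility, and the plan's own prevalence lies well below what either needs.

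Hypothesis 1a rests on screening, eligibility and enrolment rates. A miss on these two components could mean that the procedures or the other criteria are unworkable, or only that the pool had an ordinary share of depressed patients. The benchmark result cannot separate the two. A later efficacy trial would respond differently to each: by changing procedures or criteria in the first case, and by planning to screen more patients in the second.

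**Working it through.** **Inputs.** Benchmarks of ≥70% and <20% (Table 1); PHQ-9 ≥5 (III.a); up to 45% with elevated symptoms (I.a, VIII.b); ≥70% of eligible patients enrolling (Table 1); N=40 (VI.d) and approximately 50 (Aim 1). The plan derives neither benchmark, so it has no calculation to reproduce.

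**Step 1: what each benchmark requires.** Let q be the share of screened patients with PHQ-9 ≥5. The share ineligible on PHQ-9 is 1 − q, and the share meeting all criteria is at most q.
- Recruitment: q ≥ 0.70.
- Eligibility: 1 − q < 0.20, so q > 0.80.
- The most that the other criteria may exclude among PHQ-9-positive patients, if 70% are still to qualify, is 1 − 0.70/q.

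Only the 45% comes from the plan. The other values of q are assumed, to show the range.

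| q | Ineligible on PHQ-9 | <20% ineligible | ≥70% meet criteria |
|---|---|---|---|
| 0.45 | 55% | missed | missed |
| 0.60 | 40% | missed | missed |
| 0.75 | 25% | missed | met if others exclude ≤6.7% |
| 0.80 | 20% | missed (not below 20%) | met if others exclude ≤12.5% |
| 0.85 | 15% | met | met if others exclude ≤17.6% |

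For q from 70% to 80%, the eligibility benchmark fails on PHQ-9 while the recruitment benchmark can pass.

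**Step 2: chance variation.** Take 82 screened patients (Step 5), treated as independent, with PHQ-9 the only criterion anyone fails. The benchmarks then need at least 58 and at least 66 PHQ-9-positive patients. Exact binomial probabilities of meeting the recruitment and eligibility benchmarks are:
- q = 0.45: about 2 in a million, and 5 in 100 billion.
- q = 0.60: 3%, and under 0.01%.
- q = 0.75: 85%, and 15%.
- q = 0.80: 98%, and 52%.

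**Step 3: does the unstated denominator matter?** Take 45% again.
- Counted over everyone asked to be screened, with 70% consenting, PHQ-9 ineligibility is 0.70 × 0.55 = 38.5%. Getting below 20% would need consent below 0.20/0.55 = 36.4%, which misses the plan's 70% consent benchmark.
- Counted over ineligible patients only, the PHQ-9 share is 0.55/(1 − 0.45c), where c is the pass rate on the other criteria (assumed 80% to 100%, independent of PHQ-9). This gives 86% to 100%.

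The under-20% benchmark is missed on each reading.

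**Step 4: how much enrichment would be enough?** To move from pool prevalence p to screened share q, PHQ-9-positive patients must reach screening at r = [q/(1 − q)] × [(1 − p)/p] times the rate of others, over all steps combined. With p = 0.45, r = 2.33 × 1.22 = 2.85 for q = 0.70, and r must exceed 4 × 1.22 = 4.89 for q > 0.80. With assumed pools of 60% and 30%, the pairs are 1.6 and 2.7, and 5.4 and 9.3.

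**Step 5: planning effect.** Screened = N/(0.70 × yield), rounded up. For N=40, 40/0.49 gives 82 at 70% yield and 40/0.315 gives 127 at 45%. For N=50 the figures are 103 and 159. The ratio 0.70/0.45 = 1.56 means 56% more screening.

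**The case against.** The strongest reply is that the premise cannot be checked. The 45% describes ACS patients generally, or acute ones in section VIII.b, while eligibility is lifetime ACS. It also describes patients, not those who reach screening. Section III.b names routes that could raise the depressed share: psychiatry-clinic flyers, referral by psychiatrists, self-referral, opt-out before calls, and chart review. The Epic variable list is an attachment that was not supplied, and the text does not say whether the RPDR or Epic search filters on depression. Table 1 says the benchmarks draw on pilot data and earlier work. All of this stands, and it makes the finding conditional.

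A reader might infer that the benchmarks will be missed however well recruitment is run. The documents do not support that: bringing eligible patients to screening is part of recruitment, and Step 4 shows the enrichment that would be enough.

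It is also fair to say that a low yield caused by PHQ-9 is a legitimate feasibility result, that recorded reasons for ineligibility would reveal the cause, and that the plan ties no stop/go rule to a missed benchmark. These points limit the harm to interpretation. They do not remove it, because the primary benchmark would still read as a miss for a reason that may say nothing about the procedures.

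**Conclusion.** The concern holds as a conditional calibration mismatch. At the plan's own 45%, the best-case yield is 25 points below the 70% benchmark, and PHQ-9 ineligibility is 55% against a limit of under 20%. Because the plan gives the 45% as an upper figure, a lower true share would widen the gap. The conclusion assumes that the screened pool resembles that figure. At about 85% PHQ-9-positive, both benchmarks are attainable.

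It would be too much to say that the benchmarks are impossible, or that the recruitment assessment as a whole only measures depression prevalence. Two components are exposed, through one criterion. The consent, enrolment and monthly-rate benchmarks, and the under-20% test on every other criterion, are untouched. Confidence is medium because the PHQ-9 pass rate in the screened pool is unknown. The change is worth making because it is cheap and bears on what Hypothesis 1a can conclude.

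**What to change.** In Table 1, judge Hypothesis 1a on these two components as follows, and state that they are the deciding ones:
- At least 70% of screened patients with PHQ-9 ≥5 meet the remaining criteria.
- Under 20% are ineligible due to each criterion other than PHQ-9 ≥5.

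Count both among patients with a PHQ-9 score. Screening order is not stated, so report patients excluded before the PHQ-9 separately.

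Beside these, report the overall screening yield and the PHQ-9 failure rate against the existing 70% and 20% figures as descriptive results and, where recorded, by recruitment source. Section III.b keeps no personal information on inpatients who screen out, so log their source and failed criterion as de-identified counts. State the denominators for consent to screening, meeting criteria and ineligibility, and say whether the database searches filter on depression.

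The cost is rewording two rows, defining three denominators, describing the search filters and keeping a simple log. The eligibility criteria do not change. The downside is that the split benchmarks are easier to meet than the overall yield. The original figures must therefore be shown with them, and the change should be made before screening results are reviewed.
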